#### 5.1.2. Type of Participant and Disease Characteristics

3. Participants who have a positive SARS-CoV-2 test result within 7 days of randomization (by any validated diagnostic test e.g., RT-PCR, antigen-based testing on any specimen type)

AND

4. Oxygen saturation  $\geq 94\%$  on room air

AND

5. Have symptoms of COVID-19 defined by one or more of the following: fever, chills, cough, sore throat, malaise, headache, joint or muscle pain, change in smell or taste, vomiting, diarrhea, shortness of breath on exertion

AND

6. Participant to be dosed less than or equal to 7 days from onset of symptoms to dosing day (D1)

#### 5.1.3. Sex and Contraceptive/Barrier Requirements

7. No gender restrictions
8. Female participants must meet and agree to abide by the following contraceptive criteria. Contraception use by women should be consistent with local regulations regarding the methods of contraception for those participating in clinical studies.

VIR-7831  
Vir Biotechnology, Inc.

VIR-7831-5008 (GSK Study 217114)  
Amendment 4

A female participant is eligible to participate if she is not pregnant or breastfeeding, and one of the following conditions applies:

- a. Is a woman of non-childbearing potential (WONCBP) as defined in Section 10.4 Appendix 4: Contraceptive and Barrier Guidance Section [10.4](#).

OR

- b. Is a WOCBP and using a contraceptive method that is effective or highly effective, as described in Section [10.4](#) of the protocol during the study intervention period and for up to 36 weeks after the last dose of study intervention. The investigator should evaluate potential for contraceptive method failure (e.g., noncompliance, recently initiated) in relationship to the first dose of study intervention.

A WOCBP must have a negative highly sensitive pregnancy test (urine or serum as required by local regulations) before the first dose of study intervention. See Section [8.3.7](#) Pregnancy Testing of the protocol.

- If a urine test cannot be confirmed as negative (e.g., an ambiguous result), a serum pregnancy test is required. In such cases, the participant must be excluded from participation if the serum pregnancy result is positive.
- Additional requirements for pregnancy testing during and after study intervention are located in Section [1.3](#) of the protocol.

The investigator is responsible for review of medical history, menstrual history, and recent sexual activity to decrease the risk for inclusion of a woman with an early undetected pregnancy

#### **5.1.4. Informed Consent**

- 9. Capable of giving signed informed consent as described in [Section 10.1](#) which includes compliance with the requirements and restrictions listed in the informed consent form (ICF) and in this protocol.

OR

- 10. If participants are not capable of giving written informed consent, alternative consent procedures will be followed as described in [Section 10.1.3](#).

### **5.2. Exclusion Criteria**

Participants are excluded from the study if any of the following criteria apply:

#### **5.2.1. Medical Conditions**

- 1. Currently hospitalized or judged by the investigator as likely to require hospitalization for the treatment of COVID-19 in the next 24 hours
- 2. Symptoms consistent with severe COVID-19 as defined by new onset shortness of breath at rest or respiratory distress, or requiring hospitalization for continuous supplemental oxygen

VIR-7831  
Vir Biotechnology, Inc.

VIR-7831-5008 (GSK Study 217114)  
Amendment 4

3. Participants who, in the judgment of the investigator are likely to die in the next 7 days.
4. Known hypersensitivity to any constituent present in the investigational product

#### **5.2.2. Prior/Concurrent Clinical Study Experience**

5. Enrollment in any investigational vaccine study within the last 180 days or any other investigational drug study within 30 days prior to Day 1 or within 5 half-lives of the investigational compound, whichever is longer
6. Enrollment in any trial of an investigational drug, vaccine or device study for SARS-CoV-2/COVID-19 within 90 days prior to Day 1 or within 5 half-lives of the investigational compound, whichever is longer

#### **5.2.3. Other Exclusions**

7. Receipt of convalescent plasma from a recovered COVID-19 patient or anti-SARS-CoV-2 mAb within the last 3 months.
8. Participants who, in the judgment of the investigator, will be unlikely or unable to comply with the requirements of the protocol

### **5.3. Pre-Screening**

Sites may have the option to pre-screen participants to participate in the clinical study. Sites may pre-screen and administer a SARS-CoV-2 test to participants who meet the Age and Risk Factor in Section 5.1.1, and display symptoms of COVID. Pre-screening is optional and not required by any site.

### **5.4. Screen Failures**

Screen failures are defined as participants who consent to participate in the clinical study but are not subsequently randomized. A minimal set of screen failure information is required to ensure transparent reporting of screen failure participants to meet the Consolidated Standards of Reporting Trials (CONSORT) publishing requirements and to respond to queries from regulatory authorities. Minimal information includes demography, screen failure details, eligibility criteria, any protocol deviations and any serious adverse events (SAEs).

Re-screening may be performed as long as the participant is able to be dosed within 7 days after the onset of COVID-19 symptoms.

VIR-7831  
Vir Biotechnology, Inc.

VIR-7831-5008 (GSK Study 217114)  
Amendment 4

## 6. STUDY INTERVENTION(S) AND CONCOMITANT THERAPY

### 6.1. Study Intervention(s) Administered

Overview of study interventions is provided in Table 3. Detailed instructions for the administration of study drug will be provided in a separate pharmacy manual.

**Table 1: Overview of Study Intervention**

Arm Name	Sotrovimab IV
Intervention Name	VIR-7831
Type	Biologic
Dose Formulation	Solution in single-use vial
Unit Dose Strength(s)	500 mg/vial (62.5 mg/mL)
Dosage Level(s)	2000 mg once or up to 3000 mg once
Route of Administration	IV infusion
IMP and NIMP	IMP
Sourcing	VIR-7831 will be provided centrally by the Sponsor.
Dosing instructions	See Pharmacy Manual
Special instructions	Gently mix VIR-7831 prior to withdrawing from vial
Packaging and Labelling	Study intervention will be provided in a single-use vial and labelled as required per country requirement.
Current/Former Name(s) or Alias(es)	VIR-7831, GSK4182136

### 6.2. Preparation/Handling/Storage/Accountability

Instructions for the preparation of study drug will be provided in a separate pharmacy manual.

1. The investigator or designee must confirm appropriate temperature conditions have been maintained during transit for all study intervention received and any discrepancies are reported and resolved before use of the study intervention.
2. Only participants enrolled in the study may receive study intervention and only authorized site staff may supply or administer study intervention. All study interventions must be stored in a secure, environmentally controlled, and monitored (manual or automated) area in accordance with the labeled storage conditions with access limited to the investigator and authorized site staff.
3. The investigator, institution, or the head of the medical institution (where applicable) is responsible for study intervention accountability, reconciliation, and record maintenance (i.e., receipt, reconciliation, and final disposition records).
4. Further guidance and information for the final disposition of unused study intervention are provided in the pharmacy manual.

VIR-7831  
Vir Biotechnology, Inc.

VIR-7831-5008 (GSK Study 217114)  
Amendment 4

Under normal conditions of handling and administration, study intervention is not expected to pose significant safety risks to site staff. Take adequate precautions to avoid direct eye or skin contact and the generation of aerosols or mists. In the case of unintentional occupational exposure notify the monitor, medical monitor and/or Sponsor study contact.

### **6.3. Randomization**

This is an open label study and all participants enrolled will receive sotrovimab treatment. Should multiple *optional* cohorts (i.e., Cohort B1 and Cohort C) be enrolling at the same time, participants will be randomly assigned to a cohort using a predefined schema.

### **6.4. Study Intervention Compliance**

Participants will receive sotrovimab IV directly from the investigator or designee, under medical supervision. The date and start and stop times of the dose administered will be recorded in the source documents. The dose of study intervention and study participant identification will be confirmed at the time of dosing by a member of the study site staff other than the person administering the study intervention.

### **6.5. Dose Modification**

Dose modifications are not applicable. See Section 7.1 for instructions to discontinue study treatment for safety reasons.

### **6.6. Continued Access to Study Intervention after the End of the Study**

COVID-19 is an acute illness and participants are not expected to need continued access to sotrovimab after the end of the study.

### **6.7. Treatment of Overdose**

No specific treatment is recommended for an overdose. The treatment physician may provide supportive measures depending on the symptoms.

In the event of an overdose, the treating physician should:

1. Contact the medical monitor immediately.
2. Closely monitor the participant for AE/SAE and laboratory abnormalities.
3. Document the quantity of the excess dose as well as the duration of the overdosing in the CRF.

### **6.8. Concomitant Therapy**

Any medication or vaccine (including over the counter or prescription medicines, recreational drugs, vitamins, and/or herbal supplements) or other specific categories of interest that the participant is receiving at the time of enrollment or receives during the study must be recorded along with:

1. Reason for use
2. Dates of administration including start and end dates

VIR-7831  
Vir Biotechnology, Inc.

VIR-7831-5008 (GSK Study 217114)  
Amendment 4

3. Dosage information including dose and frequency

The medical monitor should be contacted if there are any questions regarding concomitant or prior therapy.

#### **6.8.1. Medication Not Permitted During the Study**

1. Receipt of convalescent plasma from a recovered COVID-19 patient or anti-SARS-CoV-2 mAb is not permitted during the study unless these are given as local standard of care if a participant is hospitalized.
2. Receipt of antivirals against COVID-19, including Paxlovid, molnupiravir, remdesivir, or passive antibody therapies are not permitted for the duration of the study unless these are given as local standard of care.
3. Receipt of investigational treatments is not permitted for the duration of the study.
4. Vaccination against COVID-19 will not be allowed 1 week prior to dosing and 8 days after dosing.

#### **6.8.2. Permitted Concomitant Medication**

All medication that the participant is receiving as local, established standard of care for acute COVID-19 is permitted.

Any concerns regarding the acceptability of potential treatments should be discussed with the medical monitor(s).

VIR-7831  
Vir Biotechnology, Inc.

VIR-7831-5008 (GSK Study 217114)  
Amendment 4

## 7. DISCONTINUATION OF STUDY INTERVENTION AND PARTICIPANT DISCONTINUATION/WITHDRAWAL

### 7.1. Discontinuation of Study Intervention

A participant will be permanently discontinued from completion of drug infusion if they experience a life-threatening, infusion-related reaction including severe allergic or hypersensitivity reactions, severe cytokine release syndrome.

In rare instances, it may be necessary for a participant to permanently discontinue study intervention. If study intervention is permanently discontinued, the participant will remain in the study to be evaluated for follow-up assessments. See the Schedule of Activities in Section 1.3 for data to be collected at the time of discontinuation of study intervention and follow-up and for any further evaluations that need to be completed.

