
VIR-7831  
Vir Biotechnology, Inc.

VIR-7831-5008 (GSK Study 217114)  
Amendment 4

Potential Risk of Clinical Significance	Summary of Data/Rationale for Risk	Mitigation Strategy
	
In the COMET-ICE study in participants with mild/moderate COVID-19 at high risk of progression, IRRs that occurred within 24 hours post infusion (pyrexia, chills, dizziness, dyspnea, pruritus, rash, and other infusion-related reaction) were reported in 6 (1%) of participants in the sotrovimab arm and 6 (1%) of participants in the placebo arm. All IRRs were nonserious, and Grade 1 or 2 severity and none led to treatment pausing or discontinuation. In the sotrovimab arm, all of the cases of IRRs were considered resolved and in the placebo arm, one participant had an event considered not resolved at the time of data cut-off. In COMET-ICE, all HSRs observed in the study were nonserious, of Grade 1 (mild) or Grade 2 (moderate) severity and reported in 2% of participants who received sotrovimab and in <1% who received placebo (9 participants treated with sotrovimab; 5 participants treated with placebo). None of the reactions in either arm led to pausing or discontinuation of the infusions. All events across both treatment groups were reported as resolved or resolving at the time of data cut-off.
 
No anaphylaxis events were reported in the COMET-ICE study in participants with mild to moderate COVID-19 not requiring hospitalization at study entry.
 
No anaphylaxis or serious hypersensitivity reactions were reported in the COMET-TAIL study in participants with mild to moderate COVID-19 not requiring hospitalization at study entry.
	
 
Investigational product will be administered in the clinic with staff trained in emergency care and resuscitation procedures with emergency care kit on hand during the study intervention administration and post-therapy observation periods.
 
Investigators will be instructed to discontinue IV infusions for participants who develop Grade 3 or higher infusion reactions.
 
If a participant experiences a Grade 2 IRR, investigators will be instructed to pause the infusion. The infusion may subsequently resume at a slower pace, at the investigator's discretion, and/or after symptomatic treatment (eg, antihistamines, IV fluids).
 
Infusion-related reactions including HSRs will be categorized as AESIs (as has been done in the past for other studies).
 

VIR-7831  

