Enhanced risk of systemic reactions including hypersensitivity reactions (SR/HSR) due to higher dose levels	
See "Infusion reactions including hypersensitivity reactions (HSR)"
 
It is possible that the risk of infusion reactions may be enhanced due to increase doses used, however as noted in the dose justification: the no-observed-adverse-effect-level for VIR-7831 was established when VIR-7831 was administered via IV infusion at 500 mg/kg (the highest dose tested) once a week for 2 weeks in cynomolgus monkeys (TX-7831-0102). Based on a preliminary population PK model for sotrovimab, the predicted <math>AUC_{inf}</math> following a 2000 mg IV dose is 21,400 <math>\mu\text{g}^*\text{day}/\text{mL}</math> and predicted <math>C_{max}</math> is 636 <math>\mu\text{g}/\text{mL}</math>. Based on the proposed 2000 mg IV dose, the margins based on nonclinical <math>C_{max}</math> and <math>AUC</math> margins of 21- and 10x, respectively, support the proposed clinical dose of 2 g IV. The <math>AUC_{inf}</math> following a 3 g IV dose is 32,100 <math>\mu\text{g}^*\text{day}/\text{mL}</math> and predicted <math>C_{max}</math> is 954 <math>\mu\text{g}/\text{mL}</math>. Based on the proposed 3000 mg IV dose, the margins based on nonclinical <math>C_{max}</math> and <math>AUC</math> margins of 14- and 7x, supporting the proposed doses up to 3000 mg.
	See Mitigation Strategy for "Infusion reactions including hypersensitivity reactions (HSR)"
Enhanced risk of systemic reactions including hypersensitivity reactions (SR/HSR) due to decreased infusion times	
See "Infusion reactions including hypersensitivity reactions (HSR)"
 
It is possible that decreased infusion times in Cohort B1 (30-minute infusion time of 2000 mg) and B2 (15-minute infusion time of 2000 mg) may enhance the possibility of a systemic reaction including hypersensitivity reactions (SR/HSR)
	See Mitigation Strategy for "Infusion reactions including hypersensitivity reactions (HSR)"

VIR-7831  
Vir Biotechnology, Inc.

VIR-7831-5008 (GSK Study 217114)  
Amendment 4

Potential Risk of Clinical Significance	Summary of Data/Rationale for Risk	Mitigation Strategy

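### The protocol gives two unreconciled sets of infusion stop and pause rules, and the stop rule in Section 7.1 is looser than the Section 2.3.1 mitigation for some Grade 3 reactions

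*Protocol*

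**What the plan says.** **Risk table (Protocol Section 2.3.1, infusion reactions row).** The stop rule is "Investigators will be instructed to discontinue IV infusions for participants who develop Grade 3 or higher infusion reactions". The pause rule is "If a participant experiences a Grade 2 IRR, investigators will be instructed to pause the infusion", after which the infusion may resume more slowly, at the investigator's discretion or after symptomatic treatment.

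**Operational section (Protocol Sections 7.1 and 7.1.1).** Participants are permanently taken off the infusion "if they experience a life-threatening, infusion-related reaction including severe allergic or hypersensitivity reactions, severe cytokine release syndrome". A second paragraph allows that permanent discontinuation may be needed in rare cases, without giving criteria. Section 7.1.1 calls for a pause when the reaction is allergic or hypersensitivity in type and mild. Restart is at the investigator's discretion or after symptomatic treatment, with no mention of rate.

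**Signposting.** Section 6.5 points to Section 7.1 for safety discontinuation and does not mention Section 2.3.1. The supplied SAP covers the earlier IM-versus-IV part of the study and sets no infusion threshold.

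**Severity scales.** Section 8.4.2 grades all adverse events by DAIDS version 2.1. Section 10.3.4 also asks for a mild, moderate or severe category for each event. Sections 7.1 and 7.1.1 use words rather than grades and name neither scale.

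**The concern.** The risk table concedes two dose-related hazards. On dose it says "It is possible that the risk of infusion reactions may be enhanced due to increase doses used". On the shorter infusions of Cohorts B1 and B2 (2000 mg over 30 and 15 minutes) it says these "may enhance the possibility of a systemic reaction including hypersensitivity reactions". For both, the mitigation is a reference back to the row that holds the Grade 3 stop and the Grade 2 pause. Those graded rules are thus part of the stated case for giving 2000 mg, or up to 3000 mg, at all.

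The section a reader is directed to for stopping does not repeat them. An investigator who consulted Section 7 alone during an infusion would find no requirement to stop for some Grade 3 reactions and no instruction for some Grade 2 reactions. What is at stake is the acute safety of the participant on the infusion. The estimation of event rates is not affected.

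**Working it through.** No arithmetic applies to the main point, so the two sets of rules are set side by side. One assumption is needed to map words to grades: that severe means Grade 3 and life-threatening means Grade 4. Those labels appear in the DAIDS laboratory table in SAP Section 6.2.2.

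| Reaction during the infusion | Section 2.3.1 | Sections 7.1 and 7.1.1 | Comparison |
|---|---|---|---|
| Grade 4 | Stop | Stop | Same |
| Grade 3 allergic or hypersensitivity, or severe CRS | Stop | Stop, if the items after *including* are read as additional triggers | Same on that reading |
| Grade 3, other type, not life-threatening | Stop | No required stop | 7.1 looser |
| Grade 2 allergic | Pause | Only mild is named | 7.1.1 silent, though a pause is the sensible inference |
| Grade 2 non-allergic | Pause; may resume more slowly | No instruction | 7.1.1 silent |
| Grade 1 allergic | No instruction | Pause | 7.1.1 stricter |
| Grade 1 non-allergic | No instruction | No instruction | Same |

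Two rows carry the point: Grade 3 reactions of another type, and non-allergic Grade 2 reactions. Neither is far-fetched. The COMET-ICE infusion-related reactions (IRRs) listed in Section 2.3.1 include pyrexia, chills, dizziness and dyspnea.

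**Can the gap be sized?** The nearest data are from COMET-ICE at 500 mg, with 6 sotrovimab participants reporting IRRs: "All IRRs were nonserious, and Grade 1 or 2 severity and none led to treatment pausing or discontinuation".

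- Denominator: Protocol Section 9.2 gives an IRR rate of 1.14%. Assume this is the sotrovimab-arm rate, 6/N. Then 6/524 = 1.145% (rounds to 1.15%), 6/525 = 1.143%, 6/528 = 1.136% and 6/529 = 1.134% (rounds to 1.13%), so N is 525 to 528. This is close to half of the 1057 randomized (528.5).
- Grade 3 or higher: 0 of N. The exact two-sided 95% upper limit is 1 − 0.025^(1/N), which is 0.700% at N = 525 and 0.696% at N = 528. The same formula at N = 50 gives 7.11%, matching Protocol Table 2.
- Grade 2: the split between Grades 1 and 2 is not given, so between 0 and 6 participants. If all 6 were Grade 2, the exact 95% interval for 6/526 is 0.42% to 2.47%.

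These limits do not measure the gap. They cover IRRs of every type, while the gap is a subset. They refer to "IRRs that occurred within 24 hours post infusion", while a stop or pause acts only during the infusion. They come from 500 mg, and the documents give no IRR rate at 2000 or 3000 mg. No count is therefore projected for this substudy.

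**The case against.** The strongest reply is that nothing conflicts. Section 7.1 lists events that require a stop; it does not say that no other event may lead to one, and its second paragraph leaves room for others. Section 2.3.1 is part of the same protocol, is worded as an instruction, and binds sites under Section 10.1.1. Read together, the rules are coherent: stop at Grade 3 or higher, pause at Grade 2, and also pause for mild allergic reactions. In addition, "Detailed instructions for the administration of study drug will be provided in a separate pharmacy manual", and that manual is not available for review; it may already carry the graded rules.

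Most of this stands. The two sets are compatible if both are applied, and a reader should not infer that a site cannot comply with both or that sites have allowed Grade 3 reactions to continue. Nothing in the documents shows either.

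Nor should a reader infer that Section 7 is looser throughout. For Grade 1 allergic reactions, Section 7.1.1 is stricter than Section 2.3.1. A rule that pauses for a mild allergic reaction also cannot sensibly mean that the infusion runs on through a moderate one. It is tempting, too, to let *life-threatening* govern the whole of the Section 7.1 sentence, which would leave every Grade 3 reaction outside it. The wording can equally be read as adding severe allergic reactions and severe CRS as triggers, so the wider gap is not established.

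What does not answer the point is the set of backstops. The second paragraph of Section 7.1, the call to the medical monitor (Section 8, item 4) and the local guidelines (Section 8.4.9.1) all help, but none contains a grade at which to stop or pause. Section 6.5 still sends the reader to the looser text.

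**Conclusion.** The inconsistency is real and should be corrected. The stop rule in Section 7.1 is looser than Section 2.3.1 for Grade 3 reactions that are non-allergic, non-CRS and not life-threatening. The pause rules differ in both directions. Confidence is high, but only about the mismatch in wording.

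The gap is small and its frequency cannot be derived from the documents. The COMET-ICE figures show that IRRs of Grade 3 or higher were not seen at 500 mg; a reader might carry the 0.70% limit over to the new doses, but nothing supports that step. The Day 8 endpoints, the sample size and the planned descriptive summaries are unaffected.

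The conclusion rests on the word-to-grade mapping above, on the more generous reading of Section 7.1, and on the available documents without the pharmacy manual or site instructions.

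**What to change.** State one rule in Sections 7.1 and 7.1.1, on the DAIDS grades of Section 8.4.2, and say that these grades rather than the Section 10.3.4 categories govern stop and pause decisions:

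- **Stop** for any infusion reaction of Grade 3 or higher, keeping the existing life-threatening and CRS stops.
- **Pause** for any Grade 2 IRR and for any Grade 1 allergic or hypersensitivity reaction.
- **Resume** at the investigator's discretion, at a slower rate if appropriate.

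Then have Sections 2.3.1 and 6.5 refer to this rule, and check that the pharmacy manual matches it.

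The cost is a protocol wording amendment and notice to sites. Under Section 10.1.1 the amendment needs IRB/IEC review, and health authority approval if it is classed as substantial. No extra participants or data are needed.
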